3.3.2.7 Wound Healing and Surgery

VEGFR inhibitors can cause wound healing complications and wound dehiscence which may occur even long after a wound has been considered healed. Therefore, surgical and traumatic wounds must have completely healed before starting cabozantinib treatment and be monitored for wound dehiscence or wound infection while the subject is being treated with cabozantinib. If possible, cabozantinib treatment should be stopped for at least 28 days prior to major surgery.

3.3.2.8 Hypertension

Hypertension is a common class effect of drugs that inhibit VEGF pathways and has been reported among subjects treated with cabozantinib.

Treatment guidelines for hypertension deemed related to cabozantinib are presented in Table 3-6. Blood pressure should be monitored in a constant position at each visit (either sitting or supine). In general, subjects with known hypertension should be optimally managed before study entry.

Decisions to decrease or hold the dose of study treatment must be based on blood pressure readings taken by a medical professional and must be confirmed with a second measurement at least 5 minutes after the first measurement. Other than for hypertension requiring immediate therapy, the presence of new or worsened hypertension should be confirmed at a second visit before taking therapeutic action. It is recommended that this second visit occurs within 1 week.

Cabozantinib should be discontinued in subjects with hypertensive crises or hypertensive encephalopathy.

Table 3-6: Management of Hypertension Related to Cabozantinib

Criteria for Dose Modifications	Treatment/Cabozantinib Dose Modification
Subjects NOT receiving optimized anti-hypertensive therapy	
> 150 mm Hg (systolic) ^a and < 160 mm Hg OR > 100 mm Hg (diastolic) and < 110 mm Hg	
 Optimize antihypertensive medications by adding new or additional antihypertensive medications and/or increase dose of existing medications. Reduce study treatment by one dose level if optimal antihypertensive therapy (usually to include 3 agents) does not result in BP <150 mm Hg systolic or <100 mm Hg diastolic If subject is symptomatic interrupt study treatment
≥ 160 mm Hg (systolic) OR ≥ 110 mm Hg (diastolic)	
 Reduce cabozantinib by one dose level^b or interrupt study treatment per investigator discretion Add new or additional anti-hypertensive medications and/or increase dose of existing medications and monitor subject closely for hypotension. If optimized antihypertensive therapy (usually to include 3 agents) does not result in BP < 150 mm Hg systolic or < 100 mm Hg diastolic, study treatment should be dose reduced further or interrupted Study treatment should be dose interrupted if upper limits of systolic BP (≥ 160 mm Hg) are sustained and not adequately manageable or if systolic BP is > 180 mm Hg or diastolic BP > 110 mm Hg, or if subject is symptomatic Re-start study treatment at the most tolerable dose and re-escalate only if BP falls to and is sustained at < 150 mm Hg systolic and < 100 mm Hg diastolic
Hypertensive emergency ^c	
 Discontinue study treatment

BP, blood pressure.

^a The investigator may decide to initiate or adjust antihypertensive treatment at a lower threshold than systolic BP >150 or diastolic BP >100 based on their clinical judgment and assessment of the individual subject.

^b Permitted dose levels are defined by individual protocols.

^c Hypertensive emergency is defined as uncontrolled elevated blood pressure with clinical evidence of progressive or impending end-organ damage (eg, myocardial infarction/ischemia, intracranial hemorrhage, cerebral ischemia, pulmonary edema,

© 2017 AGICC/Criterion Inc.

PROPRIETARY & CONFIDENTIAL

Template Final Ver. 25OCT2017

Protocol 17CRC01/EXELIXIS IST56/Version 2.0 10/27/18

encephalopathy, kidney damage).

3.3.2.9 Thromboembolic Events

Thromboembolic complications are frequent in cancer patients due to procoagulant changes induced by the malignancy or anticancer therapy including inhibitors of VEGF pathways. Deep vein thrombosis and PE have been observed in clinical studies with cabozantinib; including fatal events (please refer to the Investigator's Brochure). Subjects who develop a PE or DVT should have cabozantinib treatment held until therapeutic anticoagulation with heparins (eg, low molecular weight heparin [LMWH]) is established. LMWH are the preferred management for thrombotic events, warfarin is not recommended. Cabozantinib treatment may be resumed in subjects who are stable and have uncomplicated PE or DVT and are deriving clinical benefit from cabozantinib treatment and that anticoagulation does not place them at a significant risk that outweighs the benefit of resuming treatment per discretion of the investigator/Sponsor. During anticoagulation treatment, subjects need to be monitored on an ongoing basis for bleeding risk and signs of bleeding which may require additional or more frequent laboratory tests in accordance to institutional guidelines. If there are any signs of clinically significant bleedings, cabozantinib treatment should be permanently discontinued.

Arterial thrombotic events (eg, transient ischemic attack, myocardial infarction) have been observed in studies with cabozantinib. Subjects should be evaluated for preexisting risk factors for arterial thrombotic events such as diabetes mellitus, hyperlipidemia, hypertension, coronary artery disease, history of tobacco use, and cardiac or thromboembolic events that occurred before initiation of study treatment. Cabozantinib treatment should be discontinued in subjects who develop an acute myocardial infarction, cerebral infarction or any other clinically relevant arterial thromboembolic complication.

3.3.2.10 Proteinuria

Proteinuria is an anticipated AE with the inhibition of VEGF pathways and has been observed in cabozantinib clinical studies, and nephrotic syndrome has been reported with cabozantinib and other inhibitors of VEGF pathways. Management guidelines are provided in Table 3-7.

Cabozantinib should be permanently discontinued in subjects who develop nephrotic syndrome (proteinuria > 3.5 grams per day in combination with hypoalbuminemia and peripheral edema [hyperlipidemia and thrombotic disease may also be present]) or any other relevant renal disease.

Table 3-7: Management of Treatment-emergent Proteinuria

Severity of Proteinuria (UPCR)	Management of Proteinuria
≤ 1 mg/mg (≤ 113.1 mg/mmol)	
 No change in cabozantinib treatment or monitoring
> 1 and < 3.5 mg/mg (> 113.1 and < 395.9 mg/mmol)	
 Consider confirming with a 24-hour protein assessment within 7 days No change in cabozantinib treatment required if UPCR ≤ 2 mg/mg or urine protein ≤ 2 g/24 hours on 24-hour urine collection. Dose reduce or interrupt cabozantinib treatment if UPCR > 2 mg/mg on repeat UPCR testing or urine protein > 2 g/24 hours on 24-hour urine collection. Continue cabozantinib on a reduced dose if UPCR decreases to < 2 mg/mg. Consider holding cabozantinib treatment if UPCR remains > 2 mg/mg despite a dose reduction until UPCR decreases to < 2 mg/mg. Restart cabozantinib treatment at a reduced dose after a dose hold unless otherwise approved by sponsor. Repeat UPCR within 7 days and once per week. If UPCR < 1 mg/mg on 2 consecutive readings, UPCR monitoring can revert to protocol-specific times. (Second reading is confirmatory and can be done within 1 week of first reading.) If UPCR remains > 1 mg/mg and < 2 mg/mg for 1 month or is determined to be stable (< 20% change) for 1 month, check urine protein/creatinine per protocol or as clinically indicated.
≥ 3.5 mg/mg (≥ 395.9 mg/mmol)	
 Hold cabozantinib treatment pending repeat UPCR within 7 days and/or 24-hour urine protein. If ≥ 3.5 mg/mg on repeat UPCR, continue to hold cabozantinib treatment and check UPCR every 7 days. If UPCR decreases to < 2 mg/mg, restart cabozantinib treatment at a reduced dose and monitoring of urine protein/creatinine should continue weekly until the UPCR decreases to < 1 mg/mg. If UPCR remains > 1 mg/mg and < 2 mg/mg for 1 month or is determined to be stable (< 20% change) for 1 month, check urine protein/creatinine per protocol or as clinically indicated.
Nephrotic syndrome	
 Discontinue all study treatment

UPCR, urine protein/creatinine ratio.

3.3.2.11 Corrected QTc Prolongation

The effect of orally administered cabozantinib 140 mg qd on QTc interval was evaluated in a placebo-controlled study in subjects with MTC. A mean increase in QTcF of 10-15 ms was observed after 4 weeks after initiating cabozantinib treatment. A concentration-QTc relationship could not be definitively established. Changes in cardiac wave form morphology or new rhythms were not observed. No cabozantinib-treated subjects in this study had a QTcF > 500 ms.

Unless otherwise specified in certain protocols, only subjects with a baseline QTcF \leq 500 msec are eligible for cabozantinib research studies. Cabozantinib should be used with caution in subjects with QT prolongation risk, a history of QT interval prolongation, or who are taking antiarrhythmics or drugs known to prolong the QT interval. Concomitant treatment with strong CYP3A4 inhibitors, which may increase cabozantinib plasma concentrations, should be avoided.

If at any time on study there is an increase in QTcF to an absolute value $>$ 500 ms or an increase of $>$ 60 ms above baseline, two additional ECGs must be performed with intervals not less than 3 min apart within 30 min after the initial ECG.

If the average QTcF from the three ECGs is $>$ 500 ms or increased by $>$ 60 ms above baseline, the following actions must be taken:

- Withhold study treatment
- Immediately notify the Sponsor
- Hospitalize symptomatic subjects (eg, with palpitations, dizziness, syncope, orthostatic hypotension, a significant ventricular arrhythmia on ECG) for a thorough cardiology evaluation and management
- Consider cardiology consultation for asymptomatic subjects for evaluation and management
- Check electrolytes, especially magnesium, potassium and calcium; correct abnormalities as clinically indicated
- Check concomitant medications for any medication that may have contributed to QT prolongation, and if possible, discontinue these medications (<http://www.qtdrugs.org>)
- Repeat ECG triplicates hourly until the average QTcF is \leq 500 msec, or otherwise determined by consultation with a cardiologist or appropriate expert.

Subjects with QTc prolongation and symptoms must be monitored closely until the QTc elevation and symptoms have resolved. Study treatment may be restarted at a reduced dose level if all of the following conditions are met:

- Symptoms are determined to be unrelated to the QT interval prolongation
- The QTcF value $>$ 500 ms or increase of $>$ 60 ms above baseline is not confirmed according to protocol procedures
- Study treatment has been interrupted through a minimum of 1 week following the return of the QTcF to \leq 500 msec or return to \leq 60 ms above baseline.
- QT prolongation can be unequivocally associated with an event other than cabozantinib administration and is treatable/has been resolved
- Sponsor has reviewed all available information and has agreed to the continuation of study treatment

Following reinitiation of study treatment, ECGs must be repeated weekly for 2 weeks, then every 2 weeks for 1 month, then according to the protocol-defined time points.

All study treatment must be permanently discontinued if either of the following applies:

- Cardiac evaluation confirms that symptoms are the consequence of QT interval prolongation
- Recurrence of QTcF prolongation after reinitiation of study treatment at a reduced dose

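### In Section 3.3.2.11 the limits that start a QTcF hold, end the hourly ECGs and start the one-week restart clock do not match

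*Combined protocol and SAP*

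**What the plan says.** All the rules are in Section 3.3.2.11, Corrected QTc Prolongation.

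- **Start of the hold.** A single reading beyond either limit calls for two more ECGs. The required actions, including withholding treatment, then apply as follows: "If the average QTcF from the three ECGs is $>$ 500 ms or increased by $>$ 60 ms above baseline". Two limits are joined by *or*.
- **End of the hourly ECGs.** "Repeat ECG triplicates hourly until the average QTcF is \leq 500 msec, or otherwise determined by consultation with a cardiologist or appropriate expert". This names the absolute limit and an expert override. It does not mention the rise over baseline.
- **Start of the one-week clock.** One restart condition is "Study treatment has been interrupted through a minimum of 1 week following the return of the QTcF to" one of two levels, which the clause gives as "return of the QTcF to \leq 500 msec or return to \leq 60 ms above baseline". The two limits are again joined by *or*, and the text does not say whether both are needed or whether each belongs to its own trigger.
- **Other restart conditions.** All five listed conditions must hold. The other four are that symptoms are unrelated to the prolongation, that the excess is not confirmed by the protocol's procedures, that the prolongation has an unequivocal cause other than cabozantinib which is treatable or has resolved, and that the sponsor has reviewed the case and agreed.

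Section 4.2, exclusion criterion 15, admits patients with an average baseline QTcF of up to 500 ms.

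**The concern.** A hold that begins when either limit is crossed needs an end rule that says what must be true of each limit. Here the three rules use three different tests. If the hourly ECGs can end while the rise that caused the hold is still present, the required close monitoring does nothing for that patient. If the clock can also start at that moment, the one-week minimum no longer measures time since recovery.

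Little else in the section fills the gap for a patient without symptoms. Close monitoring until the elevation has resolved is required only for patients who have symptoms as well. Cardiology consultation for asymptomatic patients is only to be considered. The weekly ECGs begin after treatment is restarted. Table 5-1 schedules routine ECGs on odd cycles, which is every 6 weeks. One week can therefore pass with no required ECG showing that the rise has gone. With up to about 8 sites (Section 2.5), different readings of the *or* are a practical possibility.

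**Working it through.** No sample-size or power figure is involved. The check is one of logic, followed by a rough estimate of frequency.

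**Definitions.** Let b be baseline QTcF and q the on-study three-ECG average, in ms.

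- Hold: q > 500 or q − b > 60.
- Hourly ECGs end: q ≤ 500 (expert override aside).
- Clock condition, literal reading: q ≤ 500 or q − b ≤ 60.
- Clock condition, paired reading: each limit that was crossed must be regained.

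**Which patients can be held on one limit only?**

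- Rise alone: b + 60 < q ≤ 500, which requires b < 440.
- Absolute value alone: 500 < q ≤ b + 60, which requires b > 440.
- Otherwise both limits are crossed. At b = 440 or more, every rise above 60 ms also takes q above 500 ms.

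**Status at the moment of the hold, one example of each kind:**

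| Baseline → on study | Rise | Reason for hold | Hourly end point met? | Clock condition, literal | Clock condition, paired |
|---|---|---|---|---|---|
| 400 → 480 | 80 | rise alone | yes (480 ≤ 500) | met (480 ≤ 500) | not met (80 > 60) |
| 460 → 510 | 50 | absolute alone | no (510 > 500) | met (50 ≤ 60) | not met (510 > 500) |
| 440 → 510 | 70 | both | no | not met | not met |

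Enumeration in 1-ms steps, for baselines chosen between 380 and 500 ms and on-study values up to 650 ms, gave the same pattern throughout. From a baseline of 400 ms, for example, every value from 461 to 500 ms is a rise-alone hold that already meets the hourly end point. From 460 ms, every value from 501 to 520 ms is the mirror case.

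The first row has a mismatch on both readings, because the hourly end point does not depend on how the clock clause is read. The second row has one only on the literal reading. The third has none. As a matter of logic, the opposite of crossing either limit is crossing neither. A clock condition requiring both limits would be met by no patient at the time of the hold. That describes the trigger and does not recommend a clinical rule.

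**Frequency.** Section 3.3.2.11 reports a mean QTcF increase of 10 to 15 ms at 140 mg in medullary thyroid cancer. It gives no SD. Assume normally distributed changes with an SD of 15 to 25 ms:

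- Low end: P(change > 60) with mean 10, SD 15: z = (60 − 10)/15 = 3.33, P = 0.0004; 44 × 0.0004 = 0.02 patients.
- High end: mean 15, SD 25: z = (60 − 15)/25 = 1.80, P = 0.036; 44 × 0.036 = 1.6 patients.

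These are expected numbers at a single ECG time point, for any rise above 60 ms. The rise-alone group is a subset, and the documents give no baseline distribution from which to size it. On the study in medullary thyroid cancer the section also says: "No cabozantinib-treated subjects in this study had a QTcF" above 500 ms. Any trigger in that study would therefore have been on the rise alone, but the dose and population differ from this trial's.

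**The case against.** The strongest case is that the clock clause is sound when read with care. A QTcF that never exceeded 500 ms cannot return to 500 ms. For the patient at 480 ms, the only possible return is to within 60 ms of baseline. On that paired reading each limit answers its own trigger and the clock has no gap. This is a fair reading and it stands as one of two, but the text does not state it. It also leaves the hourly-ECG mismatch untouched, and once that series ends the section prescribes no ECG by which an asymptomatic patient's return would be dated.

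A second objection is that the expert clause allows the hourly ECGs to run on, and that the different end point may be deliberate. The clause does soften the point. The document gives no reason for the difference, and consultation for asymptomatic patients is optional.

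A third is that restart is guarded by four other conditions, by weekly ECGs after restart and by permanent discontinuation if the prolongation recurs. This stands, and it limits the consequence. The non-confirmation condition names the 60 ms limit and, taken literally, would bar restart for anyone held on a confirmed three-ECG average. That is a contradiction with the hold rule, so it is not a safeguard to lean on. The condition on cause can be met by a cause that is merely treatable.

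A reader might infer that every patient held for a rise above 60 ms counts as recovered at once. The documents do not support this: it cannot happen at a baseline of 440 ms or more, and below that only while QTcF stays at or below 500 ms.

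**Conclusion.** The inconsistency is real but narrow. For a patient held on the rise alone with QTcF at or below 500 ms, the hourly-ECG end point is already met at the hold, on any reading. On the literal reading of *or*, the one-week clock starts at once as well, and the mirror case (above 500 ms with a rise of 60 ms or less) also meets the clock condition, although its hourly ECGs continue. On the paired reading only the hourly-ECG mismatch remains.

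It would be tempting to conclude that such a patient could restart after one week with the rise still present. The text does not go that far: starting the clock satisfies one of five joint conditions, and sponsor agreement is among the rest.

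Events are likely to be rare. The range of 0.02 to 1.6 of 44 patients at a given ECG rests on an assumed normal distribution and SD, and on a mean from another dose and population. Sample size and the primary analysis are unaffected. The point merits correction because a cardiac safety rule followed as written can end required monitoring while the finding that caused the hold persists.

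**What to change.** In Section 3.3.2.11, reconcile the hold trigger, the end point of the hourly ECGs and the recovery wording that starts the one-week clock, so that the text states which recovery test applies to each reason for a hold: rise alone, absolute value alone, or both. Reconcile the non-confirmation restart condition at the same time, since correcting it would make the clock condition decisive in more cases. If the different end point for the hourly ECGs is intended, say so.

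Which limits and which rule should apply is for the sponsor's clinical team. The cost is a few words in one section and at most some extra ECGs in very few patients.

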3.3.2.12 Hypophosphatemia

Hypophosphatemia has been reported during treatment with cabozantinib. Serum phosphorus should be monitored frequently while receiving cabozantinib. Other causes of hypophosphatemia should be ruled out and/or these causes treated in accordance to standard of care. Mild to moderate hypophosphatemia should be managed by oral replacement including food that are high in phosphate (diary items, meats, beans) and/or oral phosphate supplements in accordance to standard clinical practice guidelines.

Clinically relevant hypophosphatemia should be managed in accordance to the dose modification guidelines as outlined in Table 3-2 and Table 3-3 or as clinically indicated.

3.3.2.13 Thyroid Function Disorders

Changes in thyroid function tests (TFTs) and hypothyroidism have been reported with cabozantinib therapy and other tyrosine kinase inhibitors as a result of altered thyroid hormone regulation by mechanisms that seem to be specific for each agent (Torino et al. 2009). Currently available data are insufficient to determine the mechanism of TFT alterations and its clinical relevance. Routine monitoring of thyroid function and assessments for signs and symptoms associated with thyroid dysfunction is recommended before initiation and during treatment with cabozantinib. Management of thyroid dysfunction (eg, symptomatic hypothyroidism) should follow accepted clinical practice guidelines and dose modification guidelines as outlined in Table 3-2 and Table 3-3.

3.3.2.14 Hemorrhagic Events

Hemorrhagic events have been reported with cabozantinib. To mitigate risk of severe hemorrhage, subjects should be evaluated for potential bleeding risk factors before initiating cabozantinib treatment and monitored for bleeding events with serial complete blood counts and physical examination while on study. Risk factors for hemorrhagic events may include (but may not be limited to) the following:

- Tumor of the lung with cavitory lesions or tumor lesions which invades, encases, major blood vessels. The anatomic location and characteristics of tumor as well as the medical history must be carefully reviewed in the selection of subjects for treatment with cabozantinib;
- Recent or concurrent radiation to the thoracic cavity;
- Active peptic ulcer disease, inflammatory GI diseases including Crohn's disease and ulcerative colitis;
- Underlying medical conditions which affect normal hemostasis (eg, deficiencies in clotting factors and/or platelet function, or thrombocytopenia);
- Concomitant medication with anticoagulants or other drugs which affect normal hemostasis;
- History of clinically significant hemoptysis.

The risk of hemorrhage in cabozantinib-treated subjects with brain metastases has not been thoroughly analyzed. Though the incidence of CNS hemorrhage events in a study of subjects with GB was higher than observed in general population of subjects with cancer treated with cabozantinib, it is not clear how the risk of hemorrhage in GB translates to a risk of hemorrhage for subjects with brain metastases. Currently, brain metastases of carcinomas are not contraindications to the use of cabozantinib, but subjects with brain metastases should be monitored with a high index of suspicion if symptoms that could be due to a CNS hemorrhage occur.

Complete healing from radiation-induced side effects should have occurred before initiating cabozantinib treatment, and cabozantinib should be discontinued in subjects with serious and life-threatening bleeding events or recent hemoptysis (≥ 2.5 mL of red blood).

